Protocol Component	Description under target trial	Description under Emulation
Eligibility Criteria	Adult inpatients receiving B-lactam therapy for culture confirmed monomicrobial invasive GAS between who can be randomized within 72h of index culture	Adult inpatients receiving B-lactam therapy for culture confirmed monomicrobial invasive GAS between the years 2015-2021 in the PINC AI™ dataset who receive anti-toxin within 3 days of index culture.
Treatment strategies	B-lactam therapy as primary therapy for GAS started within (+/-) 3 days of index GAS culture and continued for a minimum of 3 consecutive days. Adjunctive anti-toxin (clindamycin vs. linezolid) therapy started within (+) 3 days of culture.	Same as target trial.
Assignment procedures	
Patients will be randomly assigned within 3 days of culture (grace period) to clindamycin vs. linezolid. Investigators and patients and will be aware of the strategy to which they have been assigned (pragmatic, unblinded, open-label non-inferiority).
 
Switching between linezolid and clindamycin will not be permitted under the protocol.
	
Patients will be assigned to the anti-toxin therapy compatible with their observed treatment. Difference in baseline characteristics and confounding by indication will be addressed through the creation of a propensity weighted cohort.
 
Those who received both agents within the eligibility period will be excluded.

Follow up period	Starts at time of randomization (anti-toxin initiation) and ends at death, discharge to hospice, loss to follow up or 90 days, whichever occurs earliest.	Starts at time of anti-toxin initiation and ends at death, discharge to hospice or discharge from the hospital to home or facility or administrative censorship on Jan 31 st 2022.
Outcome	
Primary outcome: Time to all-cause mortality (or discharge to hospice) censored at 90 days.
 
Secondary outcome: infection attributable 90-day mortality, all-cause in-hospital mortality, 90-day disease reoccurrence, length of stay following anti-toxin administration among survivors, occurrence of CDI
	
Primary outcome: All-cause in-hospital mortality (or discharge to hospice)/ time to death (days).
 
Secondary outcome: Length of stay following anti-toxin administration among survivors, occurrence of CDI requiring treatment following anti-toxin administration.

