requiring treatment following anti-toxin administration up to 90 days, occurrence of serotonin surge syndrome while on therapy.

Causal contrast of interest	Intention-to-treat effect; per-protocol effect.	Observational analog to Intention-to-treat effect and per-protocol effect.
Analysis plan	Intention-to-treat and per protocol effects estimated via comparison of adjusted 90 day in-hospital mortality risk assigned to each treatment strategy.	
Intention-to-treat and per protocol effects estimated via comparison of adjusted in-hospital mortality risk assigned to each treatment strategy.
 
To account for confounding by indication a propensity score (PS) will be generated based on the probability of receiving linezolid using the patient and center level variables selected a priori based on clinical judgment, . Overlap weighting on a propensity-score between the two groups will be performed with downstream adjustment for ICU stay , shock and debridement/source control.

Abbreviations: CDI: Clostridioides difficile infection; GAS: Group A streptococcus.

The study was designed in accordance with the trial emulation approach described by Hernán and Robins¹⁹. The study aims to emulate a hypothetical target pragmatic multi-center, non-blinded trial.

Eligibility

Adult inpatients patients (≥ 18 y of age) with culture confirmed proven or probable (see below) invasive monomicrobial GAS in the PINC AI™ database between 2015-2021 who receive a β -lactam for a minimum of 3 days within 3 days of culture will be eligible for inclusion in the emulated trial. Patient will be included if they then receive anti-toxin therapy within 3 days of culture being drawn, as long as B-lactam therapy has been initiated prior or on the same day as antitoxin therapy.

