Proven and probable invasive GAS definitions will be adapted from the CDC ABCs case definition (<https://www.cdc.gov/abcs/methodology/case-def-ascertain.html>) using a previously used algorithm compatible with EHR data which incorporates ICD-codes³. Proven invasive GAS infection will be defined as GAS isolated from a normally sterile site, such as blood, cerebrospinal fluid, pleural fluid, peritoneal fluid, pericardial fluid, bone, joint/synovial fluid, or internal body site (e.g., lymph node, brain) OR GAS isolated from a wound culture and accompanied by necrotizing fasciitis or streptococcal toxic shock syndrome. Probable invasive GAS infection is defined as the isolation of GAS from a non-sterile site in patients with either an ICD-10 code that matches the clinical infection syndrome (eg ICD-10 for lower respiratory infection and BAL culture with GAS) or a non-specific streptococcal infection code. These include lower respiratory, musculoskeletal, genitourinary and/or skin and soft tissue samples as well other miscellaneous deep-seated infections (eg retropharyngeal abscess). Previously identified ICD-9 codes³ will be cross walked to ICD-10 codes manually with additional manual de-novo search for compatible ICD-10 codes. Final codes and culture site classification will be adjudicated by two infectious diseases clinicians.

Inclusion Criteria

- Adult inpatients patients (≥ 18 y of age)
- Monomicrobial Group A streptococcus invasive infection
- Primary therapy with a B-lactam agent (initiated before or on same day as adjunctive anti-toxin therapy)

Exclusion Criteria

Patient will be excluded if they have any of the following :

- Patients with a polymicrobial GAS culture
- Patients who allocated to the linezolid arm but have a documented linezolid resistant isolate
- Patient with concomitant MSSA/MRSA invasive infection (+/- seven days of index GAS eligibility culture)
- Patients who receive both anti-toxin agents (violation of protocol)
- Patient who don't complete at least 3 days of B-lactam (violation of protocol)

Primary Outcome measure:

in-hospital mortality defined as death during hospitalization or discharge to hospice.

Secondary outcome measures:

- Length of stay among survivors

- *Clostridioides difficile* infection

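### Entry requires three completed beta-lactam days, which can end after follow-up has begun, with no exemption for death or hospice discharge; as written the plan does not deliver its intention-to-treat analogue

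*Combined protocol and SAP*

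**What the plan says.** **Time zero.** Table 1 (Follow up period, emulation column) says follow-up "Starts at time of anti-toxin initiation and ends at death, discharge to hospice or discharge from the hospital to home or facility", or at administrative censoring.

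**Order of drugs.** The Eligibility section admits patients "as long as B-lactam therapy has been initiated prior or on the same day as antitoxin therapy". The Inclusion Criteria repeat this.

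**The three-day rule.** The Eligibility section says that patients given a beta-lactam "for a minimum of 3 days within 3 days of culture will be eligible for inclusion in the emulated trial". The Exclusion Criteria list "Patient who don't complete at least 3 days of B-lactam (violation of protocol"). Neither place exempts a patient who dies or goes to hospice before the third day.

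**Primary outcome.** It is "in-hospital mortality defined as death during hospitalization or discharge to hospice".

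**Table 1 on the same duration.** The eligibility cells state no minimum. The target trial takes patients "who can be randomized within 72h of index culture" and the emulation takes those "who receive anti-toxin within 3 days of index culture". The three days appear only under Treatment strategies, where the beta-lactam is "started within (+/-) 3 days of index GAS culture and continued for a minimum of 3 consecutive days".

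**Promised contrasts.** The Causal contrast row promises observational analogues of both the intention-to-treat and the per-protocol effect. The Sensitivity analysis section adds one line on a cloning method for potential immortal time bias, without naming a cohort or a time zero.

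**The concern.** In a randomised trial, a patient who is assigned and dies the next day stays in the intention-to-treat analysis, and the death counts. Here the same patient is removed as a protocol violator, together with the event. Survivors who are discharged, or whose beta-lactam stops, before the third day are removed too. Part of the entry condition is thus observed after time zero and depends on the outcome. Overlap weighting balances the patients who remain; it cannot bring back those excluded.

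The stake is the noninferiority conclusion on mortality. It would rest on a cohort selected partly on early survival and adherence, yet be reported as an intention-to-treat analogue against a fixed 5-point margin. Events are few: at the planned 6.5%, 207 linezolid patients yield 207 × 0.065 ≈ 13, so losing a handful of early deaths matters.

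**Working it through.** **1. Who is affected.** Count the anti-toxin day as day 0.
- Beta-lactam started on day 0: the third day is day +2.
- Started on day −1: the third day is day +1.
- Started on day −2 or earlier: three calendar days have been reached by day 0.

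The rule therefore reaches at most about two calendar days past time zero, and only for patients who started the beta-lactam on the anti-toxin day or the day before. Their share is not given.

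**2. Is there a cohort without the rule?** The other cohorts in the Sensitivity analysis section change the certainty of the GAS diagnosis or the timing of the anti-toxin. None is said to lift the three-day minimum. The cloning line does not say.

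**3. The plan's own sample size.** Inputs from Power calculation: 6.5% in both groups, 5-point margin, 1:4 allocation, 80% power, 10% dropout.
- Linezolid n = (1.645 + 0.842)² × 0.065 × 0.935 × (1 + 1/4) / 0.05² = 187.9, so 188; clindamycin 4 × 188 = 752.
- Adding 10%: 206.8 → 207 and 827.2 → 828, total 1035, as stated.

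This uses one-sided 0.05. The usual reading of the stated 2-sided 0.05 is one-sided 0.025, which gives 955 + 239 = 1194 before dropout. Both conventions are shown below because the result depends on the choice.

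**4. Illustration.** Assumed, not in the documents: true risks of 6.5% (clindamycin) and 11.5% (linezolid), a difference exactly at the margin. Let f be the share of deaths removed and g the share of survivors removed, equal in both arms.

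Observed risk = p(1−f) / [p(1−f) + (1−p)(1−g)]

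P(noninferiority) = Φ((0.05 − d)/SE − z), with d the observed difference, unpooled SE and unweighted risks.

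For f = 0.2, g = 0:
- Clindamycin: 0.052 / (0.052 + 0.935) = 5.27%.
- Linezolid: 0.092 / (0.092 + 0.885) = 9.42%.
- d = 4.15 points.
- 828/207, one-sided 0.025: SE 2.17 points; Φ(0.392 − 1.960) = 5.8%, against a nominal 2.5%.
- 752/188, one-sided 0.05: SE 2.28 points; Φ(0.374 − 1.645) = 10.2%, against a nominal 5.0%.

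With f = 0.2 and other values of g (828/207, one-sided 0.025):

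| g | Observed risks | d (points) | False noninferiority |
|---|---|---|---|
| 0.1 | 5.82% / 10.35% | 4.53 | 4.0% |
| 0.2 | 6.50% / 11.50% | 5.00 | 2.5% |
| 0.3 | 7.36% / 12.93% | 5.57 | 1.4% |

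**5. Unequal removal.** Take early deaths out as 1.3% of clindamycin and 2.6% of linezolid patients, with no survivors removed. The observed risks are (0.065 − 0.013)/(1 − 0.013) = 5.27% and (0.115 − 0.026)/(1 − 0.026) = 9.14%, so d = 3.87 points and false noninferiority is 7.6%. With the two shares swapped, d = 6.33 points and it is 0.5%.

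**The case against.** **Table 1 could be the intention-to-treat cohort and the exclusion list the per-protocol one.** The label of protocol violation and the absence of a minimum from both eligibility cells lend this some support, and the defect may be loose wording rather than a chosen analysis. But the Eligibility section puts the three days into entry to the emulated trial itself, so the text does not support two cohorts.

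**The plan already has a cloning analysis.** It shows that the sponsor sees this kind of risk. With no cohort or time zero stated, and as a sensitivity analysis only, it leaves the primary analysis unchanged.

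**The window is short and the rule is the same in both arms.** Both are true, and they limit the size of the problem. They do not make the cohort an intention-to-treat one, and an identical rule can still remove different shares of deaths and survivors by arm.

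**The magnitudes are assumed.** This stands in full. The case rests on the design, not on the illustration.

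**A stronger reading is tempting.** A reader might infer that the rule pushes the result towards noninferiority, or that it removes all early deaths. The documents support neither. The difference can shrink, stay the same or grow, and patients with three days completed by time zero are untouched.

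**Conclusion.** The point holds. As worded, the entry rule removes some primary events and some survivors after time zero, so the plan does not deliver the intention-to-treat analogue it promises. Table 1 and the criteria lists also disagree on whether the three days belong to eligibility or to treatment strategy. This must be fixed, because it touches the primary estimate and its label, and the intention-to-treat part is cheap to correct.

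The size and direction of the bias are unknown. The documents give no early-death count, no count of survivors with short beta-lactam courses, and no distribution of beta-lactam start relative to the anti-toxin. The false-noninferiority figures above show only what could happen; they rest on assumed removal shares, unweighted risks and the chosen sample size and alpha.

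A related wording issue is secondary. Table 1 (Assignment procedures, emulation) limits the exclusion for receiving both agents to the eligibility period, while the Exclusion Criteria give no limit. The latter may be shorthand, but even the narrower rule can act after time zero, for example with the first agent on day 0 and the second on day 2.

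**What to change.** **Primary intention-to-treat analogue.** Remove the three-day beta-lactam minimum from entry; a beta-lactam started on or before the anti-toxin day is enough. Classify patients by their first anti-toxin agent, and do not exclude for stopping or switching after it starts. Patients who started both agents on the same day have no first agent and can stay excluded. Leave the culture, diagnosis-code and co-infection criteria as they are, even where these become known later.

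**Sensitivity analysis and reporting.** Keep the current restricted cohort as a sensitivity analysis. Report by arm the patients and primary events that each exclusion removes. If the cloning analysis stays, state its time zero and cohort.

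**Per-protocol analogue.** Use the same cohort and count deaths and hospice discharges before the third day as events, not violations. State how a live discharge before that day is classified. Censor at deviation with inverse-probability-of-censoring weights if the database holds the daily treatment and severity covariates needed, which the documents do not show. With about 13 linezolid events expected, the weights may be unstable.

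**Reconcile** Table 1 with the Eligibility section and the Exclusion Criteria, on both the three days and the receipt of both agents.

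**Cost.** The intention-to-treat part needs SAP wording and a re-run query on the same data. The per-protocol part needs extra modelling. Some patients with short beta-lactam exposure will enter and the event rate may change, so the stated power should be rechecked.

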 - Description: *C. difficile* positive (PCR or antigen) result within same encounter downstream of the antitoxin therapy within 30 days and/or presence of a non present on admission (POA) *C. difficile* diagnosis code in conjunction with receipt of *C. difficile* therapy (PO/rectal vancomycin or PO fidaxomicin or IV metronidazole)

Statistical Analysis Plan

To account for confounding by indication a propensity score (PS) will be generated based on the probability of receiving linezolid using the patient and center level variables. Variables thought to be associated with a clinician's decision to initiate adjunctive treatment with linezolid (vs. clindamycin) and with mortality will be selected for inclusion. Overlap weighting on a propensity-score between the two groups will be performed with downstream adjustment for ICU stay, shock and debridement/source control. To take the clustered data structure into account, matching on center will be attempted if feasible, if not, propensity scores will be calculated using a mixed effects model with hospital as a random effect. Covariate balance between the two groups before and after generation of the weighted cohorts will be assessed by examining the standard mean difference for variables across the exposure categories.

Power calculation

Because no randomized clinical trials have previously compared adjunctive treatment options for GAS, the sample size estimation was derived from the largest retrospective study available³. In that study the overall in hospital mortality in adjunctive clindamycin group 6.5% in the propensity matched cohort. A published abstract, the only other published clinical data on the topic, found mortality between linezolid (n=26) and clindamycin (n=26) groups to be similar (clindamycin 11.5% and linezolid 7.7%)²¹. This was confirmed by preliminary exploration of GAS blood stream infection cases in our dataset (clindamycin 10%, linezolid 12%).

Based on a mortality rate of 6.5% in the both groups as the most conservative estimate and a noninferiority margin of 5% with 1:4 allocation ratio, 1035 patients (828 clinda + 207 Linezolid) will be needed in total to achieve 80% power with a 2-sided α level of 0.05, allowing for 10% dropout. A 5% noninferiority margin was chosen as the maximal difference in mortality between treatments that would be clinically acceptable, by consultation with infectious disease, critical care specialists within the study team.

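### Length of stay is compared only among survivors, a group selected by the primary outcome, so if mortality differs the contrast is biased toward longer stay in the arm with fewer deaths

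*Combined protocol and SAP*

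**What the plan says.** The Secondary outcome measures list gives "Length of stay among survivors". The emulation column of Table 1 has "Length of stay following anti-toxin administration among survivors, occurrence of CDI requiring treatment following anti-toxin administration", and the target-trial column has "length of stay following anti-toxin administration among survivors, occurrence of CDI". All three limit the comparison to survivors.

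The Primary Outcome measure section defines the event that removes a patient from that group: "in-hospital mortality defined as death during hospitalization or discharge to hospice". The plan does not say outright that a hospice discharge is not a survivor for the length-of-stay outcome.

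Follow-up in the emulation "Starts at time of anti-toxin initiation and ends at death, discharge to hospice or discharge from the hospital to home or facility", or at administrative censoring on 31 January 2022. Survival is therefore settled after treatment has begun.

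The Statistical Analysis Plan states: "Overlap weighting on a propensity-score between the two groups will be performed with downstream adjustment for ICU stay, shock and debridement/source control". Balance is to be checked across the two exposure groups. No method is given for length of stay, and nothing under Sensitivity analysis or Subgroup Analysis treats death or hospice discharge as a competing event. The cloning analysis addresses immortal time, which is a different problem.

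**The concern.** Weighting is meant to make the two treatment groups comparable at baseline. Selecting on survival afterwards can undo this, because survival may itself depend on the agent. Suppose one agent keeps alive some patients who would have died on the other. Those patients enter the survivor group of the first arm only. If they are sicker and stay longer than other survivors, they raise that arm's mean stay even though neither agent changes anyone's stay.

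Length of stay is one of only two secondary outcomes in the emulation. The plan gives it no formal decision role, but a reader weighing two agents of similar mortality is likely to look at it. As defined, its bias runs in favour of the arm with more deaths.

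**Working it through.** **The plan's own figure.** No figure is stated for length of stay. The arm sizes are needed below, so I checked them. The Power calculation says "Based on a mortality rate of 6.5% in the both groups as the most conservative estimate and a noninferiority margin of 5% with 1:4 allocation", with "80% power with a 2-sided α level of 0.05, allowing for 10% dropout", giving 828 + 207 = 1035.
- Clindamycin n = (z_alpha + z_beta)² × 0.065 × 0.935 × 5 / 0.05².
- One-sided 0.05: 752 + 188 = 940. Multiplying each arm by 1.10 gives 828 + 207 = 1035, an exact match.
- One-sided 0.025 (the usual reading of two-sided 0.05): 955 + 239 = 1194 before dropout, which does not lead to 1035.

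That mismatch is a separate matter. Here it only means that I show both confidence limits.

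**Size of the bias.** Assume the better agent causes no extra deaths and neither agent affects any patient's stay. Then:
- share of the better arm's survivors who would have died on the other agent = (p_high − p_low) / (1 − p_low);
- spurious difference in mean stay = share × extra days that these patients stay beyond other survivors.

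The extra days are an assumption, shown at 5, 12 and 20. The value 12 corresponds to 20 days against 8.

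| Mortality, better vs worse arm | Source | Share | +5 days | +12 days | +20 days |
|---|---|---|---|---|---|
| 6.5% vs 6.5% | planning assumption | 0 | 0 | 0 | 0 |
| 10% vs 12% | preliminary bloodstream cases | 0.02/0.90 = 2.2% | 0.11 | 0.27 | 0.44 |
| 7.7% vs 11.5% | published abstract | 0.038/0.923 = 4.1% | 0.21 | 0.49 | 0.82 |
| 6.5% vs 11.5% | planning rate plus margin | 0.05/0.935 = 5.35% | 0.27 | 0.64 | 1.07 |

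At 6.5% vs 11.5% with 30 days against 8, the shift is 0.0535 × 22 = 1.18 days. If the extra survivors stayed 5 days less than the others, the sign would reverse (−0.27 days).

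**Gaps compatible with declaring noninferiority, linezolid worse.** I used unweighted Wald limits at 828 + 207 with clindamycin mortality 6.5%.
- Two-sided 95%: at an excess of 1.0 point, SE = √(0.065 × 0.935/828 + 0.075 × 0.925/207) = 0.0202, and 0.010 + 1.96 × 0.0202 = 0.0496. The boundary is about 1.0 point.
- One-sided 95%: at 1.6 points, SE = 0.0208, and 0.016 + 1.645 × 0.0208 = 0.0502. The boundary is just under 1.6 points.
- Shares: 0.010/0.935 = 1.07% and 0.016/0.935 = 1.71%. At 12 extra days the bias is 0.13 and 0.21 days; over 5 to 20 extra days it runs from 0.05 to 0.34.
- At clindamycin 10% and linezolid 12%, SE = 0.0249 and the upper limit is 0.02 + 1.96 × 0.0249 = 6.9 points (6.1 one-sided), so noninferiority would not be declared.

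**Simulation check.** One million patients were simulated, with severity raising both death risk and stay, and no effect of treatment on any patient's stay. All inputs are assumed. At 6.5% vs 11.5%:
- survivors only: mean stay 9.43 vs 9.19 days, so the arm with fewer deaths looks 0.24 days longer;
- all patients, discharged alive by day 14: 77.3% vs 74.1%; by day 30: 92.1% vs 87.3%.

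The survivors-only contrast and the all-patient contrast point in opposite directions. At 7.7% vs 11.5% and 10% vs 12% the survivors-only shifts were 0.18 and 0.09 days.

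**The case against.** The strongest reply is that the effect is small, the outcome is secondary and openly labelled, and mortality will be reported beside it. Much of that stands. At equal mortality and equal survivor mix the bias is zero, and equal mortality is what the power calculation assumes. The planned adjustment for ICU stay, shock and source control would reduce severity differences among survivors if it is applied to this outcome. The plan does not say that it will be, and adjustment for three factors would not guarantee comparable survivors.

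A reader might infer several stronger things that the documents do not support:
- That a life-saving agent will look as if it prolongs stay. It is biased in that direction, but a true shortening could outweigh the bias.
- That the margin admits observed mortality gaps of 5 points, so that 0.64 days is typical of an accepted result. The margin applies to the confidence limit. With linezolid worse, only an excess below about 1.0 to 1.6 points passes. With linezolid better, larger gaps can pass, but the primary result then shows the benefit openly.
- That Table 1 promises an intention-to-treat analogue for length of stay. The contrast row is general, but the analysis row spells that effect out for mortality only.
- That patients still in hospital on 31 January 2022 are dropped. The plan describes this as censoring, and with index years ending in 2021 it probably affects few.

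It is also fair to say that live discharge by day 30 partly restates mortality. In the simulation its gap is 92.1 − 87.3 = 4.8 points, against a mortality gap of 5. It should therefore be read with the mortality result, not as an independent finding. This does not rescue the survivors-only contrast as a causal comparison.

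**Conclusion.** The point holds in a limited form. As defined, length of stay is compared in groups selected after treatment start by the primary outcome, and nothing in the plan handles that selection. If mortality differs and the extra survivors stay longer than average, the contrast is biased toward longer stay in the arm with fewer deaths.

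The size is modest: none if mortality and survivor mix are equal; about 0.1 to 0.2 days where linezolid is worse and noninferiority would still be declared (12 extra days assumed); and about 0.3 to 1.2 days at 6.5% versus 11.5% (5 to 22 extra days assumed), with the simulation at 0.24. These figures assume that the better agent causes no extra deaths, and the stays are not from the documents. The primary mortality conclusion is not affected. The change is worth making because it is cheap, but the study does not depend on it.

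**What to change.** Make the causal comparison an analysis of all patients in the weighted cohort:
- outcome: time from anti-toxin start to live discharge, not to hospice;
- competing event: in-hospital death or discharge to hospice;
- censoring: 31 January 2022;
- report: weighted cumulative incidence of live discharge in each arm at prespecified days (for example 14 and 30), placed beside the mortality result.

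Keep length of stay among survivors as a descriptive figure, and state that hospice discharges are not survivors.

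The cost is a few lines in the analysis plan and a standard competing-risk analysis. The dates needed are those that already define the end of follow-up. The downside is a summary less familiar than days of stay, and one that partly reflects mortality.

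### The operational C. difficile definition does not match Table 1: a positive test can count without treatment, and the code-plus-therapy branch has no date rule relative to anti-toxin

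*Combined protocol and SAP*

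**What the plan says.** The combined protocol and SAP defines this outcome in two places.

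- **Table 1, Outcome row.** The emulation column lists "occurrence of CDI requiring treatment following anti-toxin administration", with no day limit. The target-trial column has the same outcome "requiring treatment following anti-toxin administration up to 90 days".
- **Secondary outcome measures.** The operational description for C. difficile accepts a "positive (PCR or antigen) result within same encounter downstream of the antitoxin therapy within 30 days and/or presence of a non present on admission" code. It then qualifies the code: "diagnosis code in conjunction with receipt of" C. difficile therapy, followed by a list of three qualifying treatments.

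Table 1 also fixes time zero for the emulation. Follow-up "Starts at time of anti-toxin initiation and ends at death, discharge to hospice or discharge from the hospital".

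None of the five analyses under Sensitivity analysis varies the C. difficile definition.

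**The concern.** Table 1 sets two conditions: the infection was treated, and it came after anti-toxin. In the operational description each branch states only one of them. The test branch is dated but has no treatment condition. The code branch has a treatment condition but is not dated against anti-toxin. Because the branches are joined by and/or, meeting either one is enough. An analyst who programs that sentence as it stands will produce a different variable from the one Table 1 names.

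C. difficile infection is the only safety outcome carried into the emulation; the serotonin-related outcome appears only in the target-trial column. If the rule admits events that do not depend on which agent was given, a true relative difference between clindamycin and linezolid will look smaller than it is. If two programmers can read the sentence differently, the result also depends on who wrote the code.

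**Working it through.** The plan gives no C. difficile rate, power or precision figure, so there is nothing of its own to reproduce. The check is a comparison of the texts, followed by an illustration.

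**Step 1: the rule as logic.** Let T = positive PCR or antigen after anti-toxin, same encounter, within 30 days. Let C = diagnosis code not present on admission. Let R = receipt of a listed therapy. The sentence can be parsed in two ways:

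- Reading A, where therapy qualifies the code only: T or (C and R).
- Reading B, where therapy qualifies both branches: (T or C) and R.

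| T | C | R | Reading A | Reading B |
|---|---|---|---|---|
| 1 | 0 | 0 | counts | does not count |
| 1 | 1 | 0 | counts | does not count |
| 1 | 0 | 1 | counts | counts |
| 1 | 1 | 1 | counts | counts |
| 0 | 1 | 1 | counts | counts |
| 0 | 1 | 0 | does not count | does not count |

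With T = 0 and C = 0 nothing counts under either reading. The readings differ only in the first two rows, both untreated positive tests, and those rows fail Table 1's treatment condition. Reading A is the more natural one, because the therapy clause directly follows the diagnosis code.

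**Step 2: timing of the code branch.** The row T = 0, C = 1, R = 1 counts under both readings, and nothing in the sentence places the code or the therapy after anti-toxin or within 30 days. The admission condition removes disease present at admission. It says nothing about the time between admission and the first anti-toxin dose. That time can exist: Eligibility allows anti-toxin up to 3 days after culture, and no section requires the culture to be taken at admission.

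**Step 3: illustration with assumed rates.** Assume treated infection of 3.0% with clindamycin and 1.5% with linezolid (ratio 2.0, difference 1.5 points). Let u be the non-qualifying events added equally to each arm.

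Observed ratio = (0.030 + u) / (0.015 + u)

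- u = 0.005: 0.035 / 0.020 = 1.75
- u = 0.010: 0.040 / 0.025 = 1.60
- u = 0.020: 0.050 / 0.035 = 1.43

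Observed difference = (0.030 + u) − (0.015 + u) = 0.015 for every u.

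With assumed rates of 2% and 1% (ratio again 2.0), the ratio becomes 0.025 / 0.015 = 1.67, 0.030 / 0.020 = 1.50 and 0.040 / 0.030 = 1.33, and the difference stays at 1 point. If the extra events overlap slightly with the treated ones, the difference shrinks only marginally.

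**Step 4: precision for scale.** At 3.0% and 1.5%, the planned 828 and 207 patients give 828 × 0.030 = 24.8 and 207 × 0.015 = 3.1 expected events. The unweighted standard error of the log ratio is √(1/24.8 − 1/828 + 1/3.1 − 1/207) ≈ 0.60. The 95% interval around 2.0 is then about 0.6 to 6.4.

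**The case against.** The strongest reply is that the therapy clause can grammatically govern both branches, and that this reading agrees with Table 1. If so, untreated positives never count. The reading is possible, so it would be too strong to say that the plan certainly counts a bare positive test. But it is the less natural reading, the sentence does not settle the matter, and it leaves the code branch undated.

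A second reply is that Table 1 already places the whole outcome after anti-toxin and starts follow-up there, so the description need not repeat time zero in every clause. Much of this stands. A reader might infer that the plan intends to count infections arising before the first dose. The documents do not support that: an analyst would have to set aside both Table 1 statements to do so. What remains is narrower. The code branch has no rule for dating a case and no stated 30-day window.

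A third reply concerns size. The rates and the added points are assumptions, the added events are not shown to be unrelated to the drug (a positive test after anti-toxin could still be a drug effect), and the shifts lie well inside the expected uncertainty. All of that stands as a limit on practical effect. It does not make the two definitions agree.

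Finally, the passages could be reconciled the other way, by dropping the treatment condition from Table 1. That is open to the sponsor, but it would change the named outcome, and the code branch would still need a date rule.

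**Conclusion.** The point holds as a mismatch between the named outcome and its operational definition. On the natural reading, a positive PCR or antigen counts without therapy. On either reading, the code-plus-therapy branch lacks a date rule and a 30-day window relative to anti-toxin.

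The size cannot be determined from the documents. Under the assumed rates, with equal extra events in both arms, the risk ratio moves towards 1 (2.0 to between 1.75 and 1.43 for 0.5 to 2 added points) and the risk difference is essentially unchanged. Unequal additions would also move the difference, and the documents do not show which case applies. The effect is confined to this secondary safety outcome; the primary mortality analysis and the sample size do not depend on it.

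Two further inferences should not be drawn. The illustration is not evidence that the clindamycin–linezolid comparison is biased by a known amount. And the 90-day limit in the target-trial column against 30 days in the operational definition is not in itself an error: the emulation ends follow-up at hospital discharge, so the difference may be deliberate.

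**What to change.** Make the operational definition match Table 1, and state it in the same terms in both places:

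- Count a case when there is a positive test or a C. difficile code not present on admission, **and** a listed C. difficile therapy was received.
- Require the first therapy date to fall after anti-toxin start, in the same encounter and within 30 days. Apply the same rule to the test date where a test exists. Code-only cases have no test date, so the therapy date must carry the timing for them.
- Report test-positive-only cases separately as a sensitivity outcome, so that no information is lost.

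The cost is one sentence and a change to the outcome code. Test results, codes and therapy are already inputs to the definition; what is added is the use of their dates. The downside is somewhat fewer events in an outcome that is already likely to be sparse in the linezolid arm.
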